7.9.2.6 Change in six-minute walk test (6MWT) from baseline at 6 months

The six-minute walk test (6MWT) measures the distance walked in meters (m). Distance walked at each time point will be summarized as a continuous outcome. The number of subjects unable to perform the test will be tabulated by reason at each visit. Change from baseline will be summarized descriptively along with two-sided 95% confidence interval and p-value from a paired t-test. Analysis will be performed using the Attempted Implant set for all subjects able to complete the assessment at the follow-up visit.

7.9.2.7 Change in Kansas City Cardiomyopathy (KCCQ) from baseline at 30 days and 6 months

The Kansas City Cardiomyopathy Questionnaire (KCCQ) is a 23-item self-administered instrument and responses will be collected in the CRF. The domain and summary scores include: Physical Limitation, Symptom Stability, Symptom Frequency, Symptom Burden, Total Symptom Score, Self-efficacy, Quality of Life, Social Limitation, Overall Summary Score, and Clinical Summary Score. At each follow-up time point, each summary score will be summarized descriptively as continuous data. Change from baseline will be summarized descriptively along with two-sided 95% confidence interval and p-value from a paired t-test. Analysis will be performed using the Attempted Implant set.

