6.8 Missed Follow-Up Visits

Every effort should be made to ensure subjects return to the clinic for all protocol required follow-up visits, tests, and assessments. If the subject is unable to return for an in-person clinic visit, the

Investigator, or designee, should document in the subject record the reason the subject was unable to complete the visit and, if applicable, follow the requirements for deviation reporting as outlined in Section 6.10.

The investigator should also make every effort to contact the subject within the visit window to collect the subject's vital status as well as information related to potential adverse events, safety data, and hospitalizations.

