6.14 Clinical Assessment

Clinical assessment is required at each study interval. Assessments should be performed at the study center by a member of the investigative team as delegated by the PI. If the subject is unable to attend a follow-up visit, the clinical assessment can be performed by telephone, and this should be indicated on the eCRF and documented in the subject's medical record at the site. Information regarding the required variables and assessment procedures are provided in Section 13.2.

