The primary objectives of this feasibility study are as follows:

1. Characterize the spectrum of cardiac function, symptomology, and severity of aortic stenosis in the study populations,
2. Estimate event rates for potential safety and effectiveness endpoints to be evaluated in pivotal studies for the proposed patient populations, and
3. Evaluate the effect of TAVR on cardiac function, functional capacity, effort tolerance, and patient-reported quality of life in the study populations.

The study objectives and associated endpoints are intended to fully characterize the spectrum of aortic stenosis (AS) severity, left ventricular (LV) function, and symptomology of patients with moderate

symptomatic and severe asymptomatic AS, provide information on event rates for pivotal sample size estimations, and refine the entrance criteria for future pivotal studies. The full list of protocol defined endpoints are detailed in Section 7.9. Of the protocol defined endpoints, the following key study endpoints have been identified:

Key Safety Endpoints:

- All-cause mortality at 30 days and 6 months
- All stroke (disabling and non-disabling) at 30 days and 6 months
- Valve-related dysfunction requiring repeat procedure at 30 days and 6 months
- New permanent pacemaker implant (PPI) at 30 days and 6 months

Key Efficacy Endpoints:

- Cardiovascular and heart failure hospitalizations at 30 days and 6 months
- Heart failure events at 30 days and 6 months
- Change in Kansas City Cardiomyopathy Questionnaire (KCCQ) at 6 months
- Change in Six-Minute Walk Test (6MWT) at 6 months
- Change in cardiac function by echo (LVEF, Peak GLS, E:e') at 6 months

5. Investigation Plan

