7.1 Study Subjects

7.1.1 Disposition of Subjects

Subject disposition will be illustrated in a flow diagram. Subject visits will be tabulated and compliance to the visit schedule and visit windows will be summarized, and attrition will be identified and summarized. Tabulations will include the number of subjects enrolled, attempted implant, implanted, died, withdrawn, lost-to-follow-up, and completed the scheduled follow-up visit for each visit.

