7.4 Handling of Missing, Unused, and Spurious Data and Dropouts

Every effort will be undertaken to minimize missing data. Missing (accidentally, due to withdrawal, missing follow-up or loss to follow-up, etc.), unused and spurious data will remain identifiable in the database. For time-to-event outcomes, dropouts will be censored at the time of discontinuation, consistent with the Kaplan-Meier approach. Unless otherwise specified, all analyses will be based on available data and missing data will not be imputed. The number of subjects included in each analysis will be reported so that the reader can assess the potential impact of missing data.

In the case of partial dates, unknown portions will be imputed for the purposes of analysis. If only the month and year are known, the event or assessment will be analyzed as if it occurred on the 15th of the known month. If only the year is known, the event or assessment will be analyzed as if it occurred on June 30th of the known year. Imputation of partial dates is subject to the restriction that pre-implant events must occur between the date of informed consent and the date of implant and post-implant events must occur after the date of implant.

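### The change in 6MWT, a key endpoint, is estimated only in subjects able to complete the follow-up walk; as a minor point, NYHA change is given a paired t-test although eligible subjects all start in Class I

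*SAP*

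**What the plan says.** **6MWT.** SAP Section 4 lists "Change in Six-Minute Walk Test (6MWT) at 6 months" among the key efficacy endpoints. SAP 7.9.2.6 plans a descriptive summary of the change with a two-sided 95% interval and a paired t-test p-value. It defines the population as follows: "Analysis will be performed using the Attempted Implant set for all subjects able to complete the assessment at the follow-up visit".

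Three provisions make the exclusions visible:

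- SAP 7.9.2.6: "The number of subjects unable to perform the test will be tabulated by reason at each visit".
- SAP 7.1.1: "Tabulations will include the number of subjects enrolled, attempted implant, implanted, died, withdrawn, lost-to-follow-up, and completed the scheduled follow-up visit for each visit".
- SAP 7.4: "The number of subjects included in each analysis will be reported so that the reader can assess the potential impact of missing data".

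On missing values, SAP 7.4 says: "Unless otherwise specified, all analyses will be based on available data and missing data will not be imputed". No 6MWT sensitivity analysis and no rule for death is given.

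Protocol 6.18 schedules the six-month walk for implanted subjects. Protocol 13.6 has the site record distance, time and reason when a subject stops early.

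**NYHA.** Protocol 6.2.1 requires Class I at entry. SAP 7.9.2.5 plans class counts and a table of change that includes a category for death. It also plans a continuous change with a 95% interval and a paired t-test p-value. SAP 7.9.3 carries these methods to the annual visits.

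**The concern.** Whether a subject can walk at six months is itself an outcome of the treatment period. A subject who dies, or becomes too ill to walk, leaves the change estimate. The plan leaves a route for this. Protocol 6.14 says: "If the subject is unable to attend a follow-up visit, the clinical assessment can be performed by telephone". A telephone contact can yield NYHA class and events but no walk. The NYHA section just before has a category for death, and the 6MWT section has no counterpart. The SAP also does not say whether an early stopper with a recorded distance counts as having completed the test, so two programmers could reasonably differ.

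The third primary objective (Protocol 4.1) covers functional capacity and effort tolerance. In Protocol Table 1 the exercise tolerance test is ticked at baseline only. The 6MWT is therefore the only exercise test repeated after implant, and its change would inform pivotal planning.

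For NYHA, a subject in Class I cannot improve. A test of mean change can therefore detect only worsening, and its interval can extend to improvement that no eligible subject could have.

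**Working it through.** The plan states no non-performance rate, walk distance or SD for this endpoint, and the sample size of 75 was not calculated (SAP Section 6). There is no figure of the plan's own to reproduce. What follows shows how the result depends on the number of subjects who do not walk.

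**1. 6MWT: shift in the median.** Suppose w of n subjects are ranked worst. The all-subject median is then the (0.5 − w/n)/(1 − w/n) quantile of the walkers' changes. If changes are roughly normal (an assumption), the shift in SD units is Φ⁻¹[(0.5 − w/n)/(1 − w/n)]. For w = 6 and n = 75, w/n = 0.08, the quantile is 0.42/0.92 = 0.4565, and the shift is −0.11 SD.

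| n | w | shift (SD) |
|---|---|---|
| 75 | 1 | −0.02 |
| 75 | 3 | −0.05 |
| 75 | 6 | −0.11 |
| 75 | 8 | −0.15 |
| 50 | 1 | −0.03 |
| 50 | 3 | −0.08 |
| 50 | 6 | −0.17 |

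A simulation at n = 75 gave −0.017, −0.052 and −0.109 SD for w = 1, 3 and 6.

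For scale, the 95% half-width for a mean change is 1.99/√75 = 0.23 SD at n = 75 and 2.01/√50 = 0.28 SD at n = 50.

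**2. 6MWT: extreme case for the mean.** If the subjects lost are exactly those with the lowest changes, simulation at n = 75 puts the walkers' mean about 0.16 SD too high with 6 lost and 0.22 SD with 9 lost. The second figure is close to the half-width of the interval.

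**3. Why ranks rather than an assigned distance.** Assume, for illustration only, a baseline of 300 to 400 m, a walkers' gain of 20 to 30 m, and 6 of 75 unable.

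- Scored at 0 m, the all-subject mean ranges from [69 × 20 − 6 × 400]/75 = −13.6 m to [69 × 30 − 6 × 300]/75 = +3.6 m.
- Scored at half the baseline distance, it ranges from [69 × 20 − 6 × 200]/75 = +2.4 m to [69 × 30 − 6 × 150]/75 = +15.6 m.

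The score assigned can decide the sign of the result. A rank needs no such score.

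**4. Distribution-free interval for the median.** Using symmetric order statistics with Binomial(n, 0.5) coverage of at least 95%:

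| n | ordered changes | coverage |
|---|---|---|
| 75 | 29 and 47 | 96.3% |
| 60 | 22 and 39 | 97.3% |
| 50 | 18 and 33 | 96.7% |

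The lower limit is an actual walked change as long as no more than 28 of 75, or 17 of 50, rank worst.

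**5. NYHA.** Suppose all start in Class I and k of n are one class worse. The t interval is computed on k ones and n − k zeros, and is set beside the Clopper-Pearson interval for k/n.

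| k/n | t interval (classes) | exact 95% interval |
|---|---|---|
| 0/75 | undefined (SD = 0) | 0 to 4.8% |
| 1/75 | −0.013 to 0.040 | 0.0 to 7.2% |
| 3/75 | −0.005 to 0.085 | 0.8 to 11.2% |
| 0/50 | undefined (SD = 0) | 0 to 7.1% |
| 1/50 | −0.020 to 0.060 | 0.1 to 10.6% |
| 3/50 | −0.008 to 0.128 | 1.3 to 16.5% |

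Positive values mean worsening, so each negative lower limit describes an improvement that cannot occur from Class I. With 3 worse, p = 0.083 at either n. With 4 worse, p = 0.045 at n = 75 and 0.044 at n = 50. The p-value only restates whether about four or more subjects got worse. The test is planned at 30 days, 6 months and five annual visits, which makes 7 time points.

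**The case against.** The strongest reply is that the effect is probably small and already disclosed. The shifts for 1, 3, 6 and 8 of 75 are about 7%, 23%, 47% and 65% of the 0.23 SD half-width. The population is NYHA I with preserved ejection fraction and no expected early non-cardiac death, so few may fail to walk. Nothing in the documents shows that those who do not walk will have declined. Non-performers are tabulated by reason, deaths and losses are reported by visit, mortality has its own Kaplan-Meier analysis, and no hypothesis is tested. All of this stands, and it limits the severity. It does not change which subjects the reported mean, interval and p-value describe.

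The available-data rule applies across the SAP. KCCQ, also a key endpoint, has no provision for death either. That is true, but it does not answer the point for the walk.

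The remedy is also incomplete. Tests missing without a documented health reason stay outside the ranking, and someone must decide which reasons count as health-related. That stands too, so the classification needs to be fixed in advance.

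On NYHA, the class counts and change table are already planned and sound. A subject implanted in deviation from the entry criteria could start above Class I. The defect is therefore confined to the t-test, its interval and its p-value.

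**Conclusion.** The concern holds. The 6MWT estimate selects on a post-implant outcome, and the SAP discloses this without addressing it in the estimate. The direction is favourable to the device only if not walking reflects decline or death. The size is unknown. On a normal assumption the shift in the median runs from 0.02 SD (1 of 75) to 0.15 SD (8 of 75). With few non-performers the two estimates would agree, which would support the walkers' result. The unclear status of early stoppers is a defect whatever that number turns out to be.

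The NYHA t-test is unsuitable for a population that enters in Class I. It is a minor matter because this is not a key endpoint and the planned tables carry the information.

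Overall this is a modest should-fix, mainly for the 6MWT.

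**What to change.** **6MWT**

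- State that every recorded distance is used, including those from walks stopped early.
- Keep the planned mean change, labelled as covering subjects who walked at follow-up.
- Add one pre-specified sensitivity analysis in Attempted Implant subjects with a baseline walk. Rank death or inability for health reasons as the worst change, and report the median change with a distribution-free 95% interval. List in the SAP, before the six-month data are examined, which recorded reasons count as health-related.
- Show tests missing for other reasons separately and outside the ranking. These include the administrative exits under Protocol 6.7 of subjects attempted but not implanted.

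The exception clause in SAP 7.4 allows this. Protocol 10.1 rules out imputation without such a clause, so the addition should be documented under SAP 7.11.

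**NYHA**

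- Delete the paired t-test with its interval and p-value, and keep the class counts and change table.
- Add the percentage in Class II or worse among assessed subjects at 30 days and 6 months, with an exact binomial 95% interval, and carry it to the annual visits through SAP 7.9.3.
- Leave mortality to the Kaplan-Meier analysis in SAP 7.9.1.

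**Cost.** A short SAP amendment and minor programming, best done before the initial six-month analysis. The case report form is not among the documents. If its reason list does not separate health from other causes, one field can be added. Alternatively the source can be queried, since Protocol 6.8 says the investigator or designee "should document in the subject record the reason the subject was unable to complete the visit". The 6MWT result may look less favourable, and NYHA change loses its p-value.

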7.9.2.8 Change in left ventricular ejection fraction (LVEF) from baseline at 6 months

Left ventricular ejection fraction (LVEF) will be analyzed according to the data collected on the core lab echo CRF. At each time point, LVEF will be summarized descriptively as continuous data. Continuous change from baseline will be summarized descriptively along with two-sided 95% confidence interval and p-value from a paired t-test. The endpoint will be analyzed using the Implanted set.

7.9.2.9 Change in peak global longitudinal strain (GLS) from baseline at 6 months

Peak global longitudinal strain (GLS) will be analyzed according to the data collected on the core lab echo CRF. At each time point, peak GLS will be summarized descriptively as continuous data. Change from baseline will be summarized descriptively along with two-sided 95% confidence interval and p-value from a paired t-test. The endpoint will be analyzed using the Implanted set.

7.9.2.10 Change in left ventricular filling pressure (E:e') from baseline at 6 months

Left ventricular filling pressure (E:e') will be analyzed according to the data collected on the core lab echo CRF. At each time point, E:e' will be summarized descriptively as continuous data. Change from

baseline will be summarized descriptively along with two-sided 95% confidence interval and p-value from a paired t-test. The endpoint will be analyzed using the Implanted set.

7.9.2.11 Change in stroke volume index (SVI) from baseline at 6 months

Stroke volume index (SVI) will be analyzed according to the data collected on the core lab echo CRF. At each time point, SVI will be summarized descriptively as continuous data. Change from baseline will be summarized descriptively along with two-sided 95% confidence interval and p-value from a paired t-test. The endpoint will be analyzed using the Implanted set.

7.9.2.12 Change in NT-pro B-type natriuretic peptide (NT-proBNP) from baseline at 6 months

NT-proBNP will be recorded on the follow-up CRF by the investigator at each visit. At each time point, NT-proBNP will be summarized descriptively as continuous data. Additionally, the percentage of subjects with clinically-significant abnormal results (low or high) will be reported for each visit. Change from baseline will be summarized descriptively along with two-sided 95% confidence interval and p-value from a paired t-test. The endpoint will be analyzed using the Attempted Implant set.

7.9.3 Additional Outcome Measures

The following outcome measures will be also be evaluated:

1. All-cause and cardiovascular mortality annually through 5 years
2. All stroke (disabling and non-disabling) annually through 5 years
3. Cardiovascular and heart failure hospitalizations annually through 5 years
4. Heart failure events annually through 5 years
5. New York Heart Association (NYHA) functional classification at 30 days, 6 months, and annually through 5 years
6. Change in New York Heart Association (NYHA) functional classification from baseline annually through 5 years
7. Kansas City Cardiomyopathy (KCCQ) annually through 5 years
8. Hemodynamic performance metrics by Doppler echocardiography
 - Mean aortic gradient annually through 5 years
 - Effective orifice area annually through 5 years
 - Degree of total, para, and transvalvular prosthetic regurgitation annually through 5 years
 - Incidence of moderate and severe patient-prosthesis mismatch (PPM) annually through 5 years
9. Prosthetic valve thrombosis 30 days, 6 months, and annually through 5 years
10. Prosthetic valve endocarditis at 30 days, 6 months, and annually through 5 years
11. Bioprosthetic valve dysfunction (BVD) at 30 days, 6 months, and annually through 5 years
12. Bioprosthetic valve failure (BVF) at 30 days, 6 months, and annually through 5 years
13. Valve-related dysfunction requiring repeat procedure annually through 5 years

Additional Outcomes Measures 1-10 and 13:

Analysis for additional outcome measures 1-8 and 13 will follow the analysis methods defined for the same safety and efficacy endpoints at earlier timepoints described in Section 7.9.1 and 7.9.2, respectively. Prosthetic valve thrombosis and prosthetic valve endocarditis, additional outcome measures 9 and 10, will be analyzed with Kaplan-Meier analysis as described in Section 7.2. The analysis

of additional outcome measures 9 and 10 will be based on CEC adjudications using the Attempted Implant set.

Additional Outcome Measure 11 - Bioprosthetic valve dysfunction (BVD)⁽¹⁾ at 30 days, 6 months, 1 year:

Bioprosthetic valve dysfunction (BVD) is defined as meeting any of the following:

- Moderate or severe stenosis defined as any of the following:
 - Peak aortic velocity > 4 m/s OR mean aortic gradient > 40 mmHg, AND EOA < 0.8 cm²
 - Peak aortic velocity > 4 m/s OR mean aortic gradient > 40 mmHg, AND EOA ≥ 0.8 cm², AND DVI < 0.25
 - Peak aortic velocity ≤ 4 m/s and mean aortic gradient ≤ 40 mmHg, AND EOA < 0.8 cm², AND DVI < 0.25

Note: In the above, for subjects with BSA < 1.6 m², the EOA criteria for significant (moderate or severe) stenosis is < 0.6 cm². Additionally, for subjects with LVOT diameter > 2.5 cm, the DVI criteria for significant (moderate or severe) stenosis is < 0.2.

- Moderate or severe paravalvular regurgitation
- Moderate or severe transvalvular regurgitation
- Moderate or severe total regurgitation

Analysis of BVD will be based on data collected on the core lab CRF. The numerator for each time point will include the number of subjects meeting any of the components of BVD. The denominator will include any subject with BVD and subjects with no evidence of BVD having evaluable data for all 4 components. BVD will be summarized with frequency counts and percentages. The components of BVD will also be summarized. The analysis will be performed using the Implanted set.

Additional Outcome Measure 12 - Bioprosthetic valve failure (BVF)⁽²⁾ at 30 days, 6 months, 1 year

Bioprosthetic valve failure (BVF) is defined as meeting any of the following:

- Autopsy findings of bioprosthetic valve dysfunction, likely related to the cause of death, or valve-related death (i.e. any death caused by bioprosthetic valve dysfunction or sudden unexplained death following diagnosis of bioprosthetic valve dysfunction)
- Repeat intervention (i.e. valve-in-valve TAVI, paravalvular leak closure or SAVR following confirmed diagnosis of bioprosthetic valve dysfunction)
- Severe bioprosthetic valve dysfunction

A Kaplan-Meier analysis as described in Section 7.2 will be performed for BVF at 30 days, 6 months, and annually through 5 years. The analysis will use the Implanted set.

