6.7 Subject Disposition

Sites will maintain a log of subjects consented, the subject ID numbers assigned to them, and the dates of their implants (or attempted implants). Subjects who are consented but are not taken to the procedure room for implantation should be exited from the study and need not be followed beyond the date of study exit.

Subjects taken to the procedure room for implantation, and any of the following occurred: anesthesia administered, vascular line placed, TEE placed or any monitoring line placed, but do not receive a TAV for any reason should be followed for safety events for 30 days after the procedure or through the hospitalization, whichever is longer, and then exited from the study. Subjects that have their TAV explanted should be followed for safety events for 30 days after the explant procedure, or through resolution of related adverse events, whichever is longer, then exited from the study.

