- 2) Access site or access-related vascular injury (dissection, stenosis, perforation, rupture, arterio-venous fistula, pseudoaneurysm, hematoma, irreversible nerve injury, compartment syndrome, percutaneous closure device failure) *leading to death, life-threatening or major bleeding, visceral ischemia, or neurological impairment* **OR**,
- 3) Distal embolization (noncerebral) from a vascular source requiring surgery or resulting in amputation or irreversible end-organ damage **OR**,
- 4) Use of unplanned endovascular or surgical intervention associated with death, major bleeding, visceral ischemia or neurological impairment **OR**,
- 5) Any new ipsilateral lower extremity ischemia documented by patient symptoms, physical exam, and/or decreased or absent blood flow on lower extremity angiogram **OR**,
- 6) Surgery for access site-related nerve injury **OR**,
- 7) Permanent access-site related nerve injury

Minor vascular complication

- 1) Access site or access-related vascular injury (dissection, stenosis, perforation, rupture, arterio-venous fistula, pseudoaneurysms, hematomas, percutaneous closure device failure) *not leading to death, life-threatening or major bleeding¹¹, visceral ischemia, or neurological impairment* **OR**,
- 2) Distal embolization treated with embolectomy and/or thrombectomy and not resulting in amputation or irreversible end-organ damage **OR**,
- 3) Any unplanned endovascular stenting or unplanned surgical intervention not meeting the criteria for a major vascular complication **OR**,
- 4) Vascular repair or the need for vascular repair (via surgery, ultrasound-guided compression, transcatheter embolization, or stent-graft)

Percutaneous closure device failure: Failure of a closure device to achieve hemostasis at the arteriotomy site leading to alternative treatment (other than manual compression or adjunctive endovascular ballooning)

Valve Dysfunction Requiring Repeat Procedure: Any valve dysfunction that requires repeat procedure (e.g. balloon valvuloplasty, TAVR, snare repositioning, placement of vascular plug paravalvular leak, or surgical AVR)

¹¹ Refer to bleeding definitions

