4. Bioprosthetic valve dysfunction events are not reported as adverse events, unless the dysfunction is accompanied with clinical sequelae at the time of event detection, and the clinical sequelae are chronologically and physiologically associated with the dysfunction. However, prosthetic dysfunctions that are associated with adverse events, and that meet the definition of a serious adverse event, should be reported as such.

Patient-Prosthesis Mismatch (PPM)⁶³

For subjects with BMI < 30 kg/cm²

- **Moderate PPM**: EOAI = 0.85 – 0.65
- **Severe PPM**: EOAI < 0.65

For subjects with BMI ≥ 30 kg/cm²

- **Moderate PPM¹²**: EOAI = 0.70 – 0.60
- **Severe PPM**: EOAI < 0.60

Bioprosthetic Valve Failure (BVF)⁹⁰: Any of the following:

- Autopsy findings of bioprosthetic valve dysfunction, likely related to the cause of death, or valve-related death (i.e. any death caused by bioprosthetic valve dysfunction or sudden unexplained death following diagnosis of bioprosthetic valve dysfunction)
- Repeat intervention (i.e. valve-in-valve TAVI, paravalvular leak closure or SAVR following confirmed diagnosis of bioprosthetic valve dysfunction)
- Severe bioprosthetic valve dysfunction

¹² Original VARC-2 definition lists 0.90-0.60 as moderate PPM range, this definition has been updated to reflect corrected range of 0.70-0.60 for moderate PPM

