7.1.3 Analysis Sets

The enrolled population will consist of all subjects who signed the informed consent. The following analysis sets are defined within the enrolled population:

1. **Attempted Implant set:** The attempted implant data set will include all subjects with an attempted implant procedure, where an attempted implant is defined as when the subject is brought into the procedure room and any of the following have occurred: anesthesia administered, vascular line placed, Transesophageal echocardiography (TEE) placed or any monitoring line placed. Day 0 is the date of first attempted procedure.
2. **Implanted set:** The implanted data set includes all subjects with an attempted implant where the study device is implanted, defined as when the transcatheter aortic valve (TAV) is fully released from the delivery catheter system (DCS). Day 0 is the date of first attempted procedure.

In general, the primary analysis of safety, clinical outcomes, and quality of life (QoL) outcomes will be performed using the Attempted Implant analysis set and primary analysis of echo-related outcomes will be performed using the Implanted analysis set. The primary analysis population for each endpoint are detailed in Section 7.9. Analysis performed using analysis sets other than the primary would be considered supportive.

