7.9.2.3 Heart failure events at 30 days and 6 months

Heart failure events will be adjudicated by the CEC and analysis will be based on data collected on the CEC adjudication form. The endpoint will be analyzed with Kaplan-Meier survival analysis according to Section 7.2 for each time point. The primary analysis will use the Attempted Implant set.

7.9.2.4 Hemodynamic performance metrics by Doppler echocardiography at discharge, 30 days, and 6 months

The following hemodynamic performance metrics by Doppler echocardiography will be reported at discharge, 30 days, and 6 months:

- Mean aortic gradient
- Effective orifice area
- Degree of total, para, and transvalvular prosthetic regurgitation
- Incidence of moderate and severe patient-prosthesis mismatch (PPM)

Endpoint Definitions:

Mean aortic gradient will be reported in units of mmHg.

Effective Orifice Area (EOA) in cm² will be derived according to the following formula

$$EOA = LVOT\ diameter^2 \times 0.785 \times (LVOT\ VTI / Aortic\ valve\ VTI)$$

Where: LVOT VTI is the velocity time integral of the left ventricular outflow tract in cm, and aortic valve VTI is the velocity time integral of the aortic prosthesis in cm.

Degree of total, para, and transvalvular prosthetic regurgitation will be reported in categories of none, trace, mild, moderate, and severe.

Patient-prosthesis mismatch (PPM)⁽¹⁾ is defined as follows:

For subjects with body mass index (BMI) < 30 kg/cm²

- **Moderate PPM:** EOAI = 0.85 – 0.65
- **Severe PPM:** EOAI < 0.65

For subjects with BMI ≥ 30 kg/cm²

- **Moderate PPM:** EOAI = 0.70 – 0.60
- **Severe PPM:** EOAI < 0.60.

Note that in the above, Effective Orifice Area Index (EOAI) in cm²/m² is defined as EOAI = EOA/BSA where EOA is the effective orifice area in cm² and BSA is the body surface area in m².

Analysis Methods:

Data for all endpoints will be reported on the core lab echo CRF. Mean aortic gradient and EOA will be summarized descriptively as continuous outcomes at each time point. Change from baseline in mean aortic gradient and EOA will also be summarized descriptively along with two-sided 95% confidence interval and p-value from a paired t-test. The degree of total, para, and transvalvular prosthetic regurgitation and incidence of moderate and severe PPM will be summarized with frequency counts and percentages at each follow-up time point. Analysis of each hemodynamic performance outcome will use the Implanted set.

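### BVD is reported only as prevalence at each visit, so later percentages can understate how many study valves ever became dysfunctional

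*SAP*

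**What the plan says.** Four rules together decide how BVD is counted.

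- **Source and numerator (SAP 7.9.3, measure 11).** "Analysis of BVD will be based on data collected on the core lab CRF", and "The numerator for each time point will include the number of subjects meeting any of the components of BVD". The result is a count and percentage. Bioprosthetic valve failure (BVF), the next measure, is instead analysed by Kaplan-Meier.
- **Denominator (same place).** "The denominator will include any subject with BVD and subjects with no evidence of BVD having evaluable data for all 4 components".
- **Analysis set (SAP 7.1.3).** "The implanted data set includes all subjects with an attempted implant where the study device is implanted". Membership is fixed once the valve is released at implantation, and a later reintervention does not change it. SAP 7.4 adds that analyses use available data without imputation.
- **Follow-up.** Protocol 5.1 keeps all implanted subjects on the schedule for five years. Protocol 6.7 makes an exception for explants: "Subjects that have their TAV explanted should be followed for safety events for 30 days after the explant procedure" (or until related adverse events resolve, if longer), after which they exit.

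The haemodynamic summaries in SAP 7.9.2.4 work the same way: "Analysis of each hemodynamic performance outcome will use the Implanted set". SAP 7.9.3 carries those methods to five years as measure 8.

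The protocol foresees reintervention. Section 13.8.1 defines valve dysfunction requiring repeat procedure as "Any valve dysfunction that requires repeat procedure (e.g. balloon valvuloplasty, TAVR, snare repositioning" and further examples: a plug for paravalvular leak and surgical replacement. Section 13.8.2 defines a second valve placed inside the first, during or after the index procedure.

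**The concern.** The subjects whose study valve became dysfunctional are the ones most likely to have something done about it. If treatment works, the next core lab echo describes the study valve plus the repair, and the visit table records the subject as evaluable and free of BVD. If the valve is explanted, there is no later echo and the subject disappears from the table. Dysfunction found on an unscheduled echo and corrected before the next scheduled visit may never appear in it.

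Estimating event rates for pivotal studies is a stated objective (Protocol 4.1, SAP 4). Someone planning a pivotal trial could take the late BVD percentage as the share of study valves that became dysfunctional. Under these rules it is the share showing dysfunction on that visit's echo.

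**Working it through.** **1. Follow a subject through the rules.** No sentence in either document deals with echoes after a reintervention, so the defaults apply.

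| Course after BVD is found | At later visits in the BVD table |
|---|---|
| No repeat procedure, BVD persists | Numerator and denominator |
| Balloon, snare, plug or valve-in-valve; later echo normal | Denominator only, as no BVD |
| Same procedures; later echo still meets a BVD criterion | Numerator and denominator |
| Explant | In neither |

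**2. Arithmetic.** The plan has no figure to reproduce: the 75 subjects were not derived statistically (Protocol 10.7, SAP 6), and no BVD or reintervention rate is given. The inputs are n = 75 from the documents and the following assumed counts:

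- b = subjects with BVD on the current visit's echo
- k = subjects with earlier BVD, corrected with the study valve in place and a normal echo now

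As tabulated: b/n. Ever affected: (b + k)/n. Gap: k/n. Intervals are exact (Clopper-Pearson) 95%.

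With b = 2 and n = 75, the table shows 2/75 = 2.7% (0.3 to 9.3) whatever k is:

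| k | Ever affected | Gap (points) |
|---|---|---|
| 1 | 3/75 = 4.0% (0.8 to 11.2) | 1.3 |
| 2 | 4/75 = 5.3% (1.5 to 13.1) | 2.7 |
| 3 | 5/75 = 6.7% (2.2 to 14.9) | 4.0 |
| 5 | 7/75 = 9.3% (3.8 to 18.3) | 6.7 |

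Each such subject is worth 1/75 = 1.3 points, or 1/50 = 2.0 points if only 50 are evaluable. If the k = 2 subjects had been explanted instead, the table would show 2/73 = 2.7% (0.3 to 9.5), almost the same figure by another route.

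**3. Does dropping post-procedure echoes solve it?** For BVD it does not: b/(n − k) = 2/73 = 2.7%, still far from 5.3%. For gradients it can go either way (all gradient values assumed):

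- If the gradient was 45 mmHg before the procedure and 10 to 20 mmHg after, using the later value instead lowers the mean by k × (45 − post)/75. That is 0.33 to 0.47 mmHg for one subject and 1.67 to 2.33 mmHg for five.
- If 73 subjects are at 8 mmHg and 2 treated subjects at 20 mmHg, the all-data mean is (73 × 8 + 2 × 20)/75 = 8.3 mmHg. Dropping the two gives 8.0 mmHg, a better-looking result.

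A cumulative count is therefore what addresses BVD, and exclusion is useful only as a supportive view.

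**The case against.** The strongest reply is that the failures are reported elsewhere, and this stands.

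- Valve-related dysfunction requiring repeat procedure covers all the procedures discussed here. It is a key safety endpoint at 30 days and 6 months and measure 13 annually to five years. It is CEC-adjudicated and analysed by Kaplan-Meier to first event, so no later echo can erase it.
- BVF, also by Kaplan-Meier, includes severe dysfunction and "Repeat intervention (i.e. valve-in-valve TAVI, paravalvular leak closure or SAVR following confirmed diagnosis of bioprosthetic valve dysfunction". Moderate dysfunction treated by balloon or snare is outside that list but still within measure 13.
- A second valve at the index procedure fails device success, which requires a single prosthesis (SAP 7.9.2.1).

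A reader might infer that rescued failures vanish from the report, or that the bias is always favourable. The documents support neither. The endpoints above retain the procedures, and an unsuccessful procedure still counts as BVD. A second valve could even leave a higher gradient or smaller orifice area than before.

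It is also fair to say that visit prevalence is a legitimate estimand, that prevalence and ever-affected answer different questions, and that BVD is an additional descriptive measure with no hypothesis attached. Protocol 13.8.3 bases valve dysfunction reporting on core lab results, so counting a procedure as BVD without core lab evidence would alter the definition.

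What remains is narrower. Measure 13 counts procedures, and BVF counts severe dysfunction and selected interventions. Neither gives the cumulative frequency of BVD as defined, and the one table that reports BVD can fall when a dysfunctional valve is treated.

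**Conclusion.** The point holds as a gap in how one outcome is summarised. By the plan's default rules, later BVD percentages can understate how many study valves became dysfunctional. The gap is 1.3 points per successfully treated subject at n = 75, for example 2.7% at the visit against 5.3% ever.

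This rests on assumed counts and on all 75 subjects still being evaluable. Deaths, withdrawals and unreadable echoes would shrink the denominator and enlarge each subject's weight. It also assumes the procedure succeeds or the valve is explanted. If reinterventions are rare the effect is small, and the intervals above overlap widely.

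It would be tempting to conclude that post-procedure echoes should be removed from the main haemodynamic summaries. The documents do not require that, and the working shows it barely moves BVD and can flatter the mean gradient.

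**What to change.** In SAP 7.9.3, measure 11:

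- Keep the visit prevalence.
- Add cumulative BVD through each time point: time to first core-lab BVD on any scheduled or unscheduled echo, with death as a competing event.
- Add a separately labelled composite that also counts a repeat procedure or explant for valve dysfunction as an event, so that the core-lab definition stays intact in the first version.

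In the BVD tables and the haemodynamic tables (SAP 7.9.2.4 and measure 8):

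- Show the number of subjects with a reintervention, and the number explanted, before each visit.
- Keep the all-data summary as the main one, and add a supportive summary without post-reintervention echoes.
- Note that ballooning during the implant procedure is not a reintervention, as Protocol 7.1 already says.

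In the same edit, reconcile the sub-headings for measures 11 and 12, which stop at 1 year, with the list of measures, which runs to 5 years.

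No new data are needed: CEC adjudications, core lab echoes and study exits are already collected. The cost is SAP wording, one derived reintervention date, one extra analysis and a slightly less favourable late BVD figure.
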